a) Bioluminescence imaging of control and GVHD mice 3 days after HCT revealed homing of luciferase-positive donor T cells to secondary lymphoid organs such as the spleen, cervical lymph nodes (CLN), and mesenteric lymph nodes (MLN) in GVHD mice. **b)** Representative $[^{18}\text{F}]\text{F-AraG}$ PET/CT images (10 minute static scan; 60-70 minutes post-tracer administration; $\sim 200 \mu\text{Ci}$) at this time point showed visibly higher tracer uptake in the CLN of GVHD mice versus control mice ($n=3$ per group). **c)** Quantitative region of interest PET image analysis of the CLN corroborated our qualitative assessments, demonstrating significantly ($*p < 0.05$) higher tracer uptake in the CLN of GVHD mice versus control mice (%ID/g; percentage injected dose per gram of tissue). **d)** Biodistribution studies (90 minutes after tracer administration) also supported our imaging findings showing significantly ($*p < 0.05$) higher tracer uptake in CLNs in GVHD versus control mice. Significantly ($*p < 0.05$) higher tracer uptake was also apparent in the T-cells harboring MLN and a trend ($p=0.12$) towards higher uptake was seen in the spleen. Data in all graphs are expressed as mean \pm SD.

At day 10, at the peak of T cell activation, $[^{18}\text{F}]\text{F-AraG}$ PET/CT images showed an even more apparent increase in tracer accumulation in the CLN of aGVHD compared to control mice (Fig. 8b), which was quantitatively confirmed via PET image analysis (Fig. 8c). Tracer biodistribution analysis revealed significantly lower tracer uptake in the spleen at this time point ($p < 0.05$, Fig. 8d), but higher uptake in both the CLN and the MLN ($p < 0.05$ and $p < 0.01$, respectively). Amongst aGVHD mice, we also showed significantly higher BLI and PET signal within the CLNs at day 10 versus day 3 ($p < 0.05$; Fig. 8e), indicating promise for monitoring disease burden via this surrogate imaging biomarker. These findings were recently published in Cancer Research (77(11); 2893–902, 2017).

[figure not shown]

Figure 8: Bioluminescence and $[^{18}\text{F}]$ -AraG PET Imaging of Donor T Cell Dynamics During the Peak of T Cell Activation in a Mouse Model of acute GVHD

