2.6 Study Design

Study participants will consist of healthy volunteers for extended studies on radiotracer behavior and patients belonging to a GVHD group. Two patient categories exist within the GVHD group-those highly suspected to have acute GVHD and those that are at high risk for developing acute GVHD. We will recruit healthy volunteers through local advertising. We will recruit high risk and confirmed GvHD patients from the Bone Marrow and Transplantation Clinic at the Stanford Cancer Institute.

Normal subjects will be recruited by publicly disseminating the information about the clinical trial through printed media such as a flyer, or by sending out an email to the Stanford community. We will ask for volunteers. A consent form for healthy volunteers is also included. Patients will undergo preliminary evaluation to ensure eligibility, receive and sign an informed consent, be enrolled in the trial, and then have [¹⁸F]F-AraG PET/CT.

Highly suspected acute GVHD patients will be scanned following biopsy (taken to confirm acute GVHD). The staging and grading of the disease using the Glucksberg grade and International bone marrow Transplant Registry Severity Index (IBMTR) at time of enrollment will be noted. Their consent for a PET-CT scan will be obtained prior to biopsy. Biopsy tissues of consented patients will be analyzed further for T cell involvement.

High-risk patients (recipients of myeloablative or reduced intensity allogeneic transplants using either bone marrow or peripheral blood stem cells from HLA-matched or HLA-mismatched related or unrelated donors-protocols 9917, 9142, 9022, 9924) will have to sign consent forms

before they undergo a transplant. All those that consent will undergo a PET-CT scan day 4 \pm 2 days post transplant. Additionally these patients will be scanned again between day 14-21 post transplant. Follow up on these patients will note those that go on to develop aGVHD and the clinical end point will be correlated to the scans to verify any predictive potential of the radiotracer.

For both GVHD groups-results of the scan will be compared to biopsy results and immunohistochemical staining of the biopsy samples for T cells.

Investigational agent: $[^{18}\text{F}]\text{F-AraG}$ will be formulated in a sterile and pyrogen-free isotonic solution will be administered in a single slow IV injection.

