9.1.1 Primary Outcome Measurement Methods

Static images acquired will be used to determine the bio-distribution of the imaging agent in the GVHD groups. Past images as well as newly acquired data from healthy subjects will be used as comparisons. Regions of interest will be drawn on various organs such as the liver, cervical lymph nodes and gut and quantified using imaging software (e.g. Inveon Research Workplace or Amide). In addition any areas that show up differently in the GVHD groups, to the normal bio-distribution seen in healthy subjects will be identified and ROIs will also be drawn over these regions.

Bio-distribution data will be expressed as % injected dose/gram (%ID/g) and/or as standard uptake values (SUV) with respect to the organ being studied. In the high suspected aGVHD group, [¹⁸F]F-AraG PET results will be compared to any grades and scores of aGVHD severity attributed to subjects. In the case of the high-risk group, after the second scan, patients will be monitored for development of aGVHD and the clinical endpoint (whether or not the high risk patient develop aGVHD) will represent the primary outcome variable. In addition, IHC analysis of biopsies taken in either GVHD group will help in the interpretation of the primary results and thus potentially support interpretation of the PET data. The IHC analysis will involve determining the amount of cell death or T cell infiltration and activation.

Vital signs and blood laboratory data collected before and after the i.v. injection of [¹⁸F]F-AraG will allow evaluation of any unexpected side effects.

To measure plasma radioactivity, whole blood sample will be centrifuged. The radiolabeled tracer concentration in whole blood, pellet post centrifugation and plasma will be measured by a gamma well counter (1-min per sample). The counting rates measured by the well counter will be converted to the PET equivalent counts using a conversion factor from a weekly phantom cylinder study. The counts should be decay corrected back to the injection time.

Plasma parent tracer and metabolite concentrations will be determined using solid phase extraction combined with HPLC technology.

Clinical assessment of disease severity will be made by the aGVHD grade. Staging and grading of the disease will be performed by Clinicians at the Bone Marrow and Transplant Clinic using the Glucksberg grade and International bone marrow Transplant Registry Severity Index (IBMTR) at time of enrollment and imaging.

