9.1.2 Primary Outcome Measurement Time Points

Duration of the follow up will extend to 6 months post final scan for all aGVHD subjects by chart review.

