10.5.2 Analysis Plan

Although the study will have low power due to the constrained sample size, in addition to descriptive statistics we will perform the following statistical analyses:

- In the highly suspected group:
Spearman rank correlation between median or maximum SUV values across ROIs and disease severity
- In the high-risk group:
Spearman rank correlation between SUV values in the first and second scans prediction of disease status at end of follow-up (aGVHD or no aGVHD) from SUV values of the first and second scans (using logistic regression)

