10.7 Sample Size

This is a pilot study, for the first time in GVHD patients including up to 25 GVHD patients (roughly half each in the highly suspected and high-risk groups). An additional 5 healthy volunteers are also being included to add to existing bio-distribution data crucial to understand tracer characteristics. While the small sample size provides insufficient power for formal statistical tests, we will examine the data and expect a high level of agreement between uptake of [¹⁸F]F-AraG with severity and progression of disease, and IHC results from biopsies

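### Arm 2: the scan 1–scan 2 Spearman leaves out aGVHD and has no fixed direction if the tracer works, and the logistic regression on both scans has no stated form and often cannot be fitted in about 12 patients

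*Combined protocol and SAP*

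**What the plan says.** Section 2.6 has high-risk patients scanned on day 4 ± 2 after transplant, and then: "Additionally these patients will be scanned again between day 14-21 post transplant". The purpose is that "the clinical end point will be correlated to the scans to verify any predictive potential of the radiotracer". Section 9.1.1 states that for this group "the clinical endpoint (whether or not the high risk patient develop aGVHD) will represent the primary outcome variable". On follow-up, section 9.1.2 says: "Duration of the follow up will extend to 6 months post final scan".

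Section 10.5.2 lists two analyses for this group. They run together in the extracted text but read as separate items. The first is a "Spearman rank correlation between SUV values in the first and second scans", a statistic in which aGVHD does not appear. The second is a logistic regression that uses the SUVs of both scans to predict whether the patient has aGVHD when follow-up ends.

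It does not say whether the two scans enter one logistic model or two. It names no region and no SUV summary for Arm 2, although it names the median or maximum across regions for the highly suspected group. Section 9.1.3 speaks of reading SUVmax, and section 8.2 has mean, maximum and minimum recorded. No section defines a difference, ratio or percentage change between the scans. Section 10.7 expects uptake to agree "with severity and progression of disease, and IHC results from biopsies".

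**The concern.** Two scans per patient give three natural candidate predictors of aGVHD: the early value, the later value and the change between them. The first listed analysis uses none of them as a predictor. It asks only whether patients keep their rank order from one scan to the next. A tracer that shows nothing but stable background can score high on it, and so can a tracer that works.

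That leaves the whole Arm 2 question to the logistic regression. If the scans are modelled separately, change is not examined. If they are modelled jointly in about 12 patients, the fit may break down, most readily when the tracer separates the groups well. Each second session costs the patient a further injection and 5.7 to 6.3 mSv (section 7.1), so its analysis should be fixed before the data are seen.

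**Working it through.** The plan gives no power, significance level or effect size, so there is no stated figure to reproduce.

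**Inputs from the documents**
- Up to 25 GVHD patients, roughly half in each group (10.7): 12 to 13 in Arm 2.
- GVHD incidence 20–50% with related donors and upwards of 70% with matched unrelated donors (2.1).
- Healthy cervical-node SUVmean 5.2 ± 1.15 (Table 1): CV = 1.15/5.2 = 0.221.
- Mouse cervical node, aGVHD versus control at day 3: about 1.4-fold (2.2).

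**Assumptions**
- 6 patients with and 6 without aGVHD.
- Total SD of log SUV 0.22, of which the within-patient SD w is 0.05, 0.10 or 0.15.
- Fold increases in aGVHD patients as tabulated; 1.4 borrows the mouse figure and 2.0 is assumed.
- Two-sided Mann-Whitney test at 5%.

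**Step 1. Model.** log SUV(scan j) = person effect + noise(SD w) + ln(fold j) if aGVHD. The log ratio removes the person effect and has SD w√2. A single scan has SD 0.22.

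**Step 2. Results** (w = 0.05 / 0.10 / 0.15)

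| Fold at scan 1 / scan 2 | Mean Spearman | Scan 2 alone, power | Log ratio, power |
|---|---|---|---|
| 1.0 / 1.0 | 0.91 / 0.73 / 0.48 | about 4–5% | about 4–5% |
| 1.0 / 1.4 | 0.66 / 0.54 / 0.37 | about 60% | 100% / 93% / 63% |
| 1.4 / 1.4 | 0.94 / 0.83 / 0.67 | about 60% | about 4% |
| 1.4 / 2.0 | 0.88 / 0.82 / 0.72 | about 99% | 100% / 96% / 70% |

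The Spearman falls if the signal appears only at scan 2. It rises or stays about level if the signal is already there at scan 1.

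**Step 3. Cross-check.** A second simulation used SUV 5.2 ± 1.15, between-scan correlation 0.7 and 50% aGVHD. The large-sample Spearman was 0.68 with no effect, 0.53 with 1.0/1.4, 0.80 with 1.4/1.4 and 0.81 with 1.4/2.0. At 12 patients, over correlations of 0.5 to 0.9, the sampling SD of one coefficient was about 0.10 to 0.27. Shifts of 0.1 to 0.2 are therefore hard to read in either direction.

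**Step 4. Is change inside the logistic model?** In a joint model, b1·S1 + b2·S2 = (b1 + b2)·S1 + b2·(S2 − S1). Both forms fitted to one simulated data set gave the same log-likelihood (−230.536) and the same fitted probabilities. A joint model therefore contains the change, and on log SUV it contains the log ratio. Two separate models do not.

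**Step 5. Can the joint model be fitted?** The smaller outcome group runs from 12 × 0.2 = 2.4 to 13 × 0.5 = 6.5 patients, which is 1.2 to 3.25 per predictor. Under the Step 1 model, the share of trials with complete or quasi-complete separation (no finite maximum-likelihood estimate) was:
- no effect: 1–2%
- 1.0/1.4, w = 0.10: about 66%
- 1.4/2.0, w = 0.10: about 92%

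At w = 0.05 both of the last two are 100%. At w = 0.15 they are about 40% and 86%.

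**Step 6. When does the ratio beat scan 2?** If the signal is only at scan 2, the ratio is more precise while w√2 < 0.22, that is w < 0.156. With 2 or 3 events among 12 patients, its power at w = 0.10 is 61–80% rather than 93%. If uptake is raised equally at both scans, the ratio has chance-level power.

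**The case against.** The strongest defence is that section 10.5.2 does relate both scans to aGVHD. A reader who stops at the Spearman might infer that the change is never analysed against the outcome. The documents do not support that: the logistic regression is there, and in joint form it uses the patient's first scan as reference (Step 4).

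A reader might also infer that the Spearman must fall if the tracer works. That holds only if nothing is visible at scan 1. The mouse data point to an early signal as well: the 1.4-fold figure is aGVHD against control at day 3, not a rise over time.

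Nor do the mice show within-subject change. Section 2.2 reports that "we also showed significantly higher BLI and PET signal within the CLNs at day 10 versus day 3", but animals were killed 90 minutes after the tracer, so the two days compare different animals. The text gives no fold change between the days.

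Finally, the plan calls itself a low-powered pilot and sets no favourable value for the Spearman, so it cannot be said that a high value would be taken as success.

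All of this stands, and it limits the point. It does not supply the model form, the region or the SUV summary, and it offers no fallback when the logistic fit fails. Pilot status excuses low power; it does not excuse leaving the predictor unnamed.

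**Conclusion.** The point holds as a moderate specification gap. The Spearman cannot answer the Arm 2 question, because it omits aGVHD and its direction depends on when the signal appears: at w = 0.10 it moves from about 0.73 to 0.54 or to 0.83. The logistic regression can answer it in principle, but its form is unstated. As an ordinary two-predictor fit it would be separated in about 66% to 92% of trials at that SD when uptake rises between scans.

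A reader might conclude that the ratio should replace the single-scan values. The results do not support that: with 1.4-fold uptake at both scans the ratio has about 4% power, against roughly 60% for either scan alone. Both measures are needed.

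The sizes rest on assumed human fold changes, an assumed within-patient SD, a 6-to-6 split and the healthy-volunteer spread applied to patients. The lack of a fixed direction and the equivalence in Step 4 do not depend on those particular values.

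**What to change.** In section 10.5.2, for the high-risk group:

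1. Label the scan-to-scan Spearman as descriptive, reported as repeatability in patients who stay free of aGVHD.
2. As the outcome analysis, compare patients who do and do not develop aGVHD on (a) scan 2 SUV and (b) the per-patient log ratio of scan 2 to scan 1 SUV. Use a rank test and AUC with an exact or bootstrap interval.
3. Name the organs and one SUV summary in advance. Keep cervical node, spleen and gut separate, because in the day 10 mice node uptake was higher and spleen uptake lower than in controls.
4. Keep scan 1 SUV as a supporting analysis.
5. State whether any logistic model is joint or separate, and fit it by a penalised (Firth) method.

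The cost is SAP wording and analysis of data already being collected. There are three downsides. Patients without a second scan drop out of the ratio. The ratio shows nothing if uptake is raised and flat from scan 1, which is why scan 2 SUV must stay beside it. There are also a few more exploratory comparisons to report as such.

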3 PARTICIPANT SELECTION AND ENROLLMENT PROCEDURES

3.1 Inclusion Criteria

This study will enroll three cohorts of participants: healthy volunteers, patients highly suspected to have acute GVHD and requiring systemic therapy, and patients at high risk for developing acute GVHD. For patients highly suspected to have acute GVHD and requiring systemic therapy, biopsy of involved tissue is encouraged to support the clinical diagnosis- this will normally be taken from the gastrointestinal tract. T cell staining will be incorporated in the immunohistochemical analysis of the tissue.

Participants must meet all of the following relevant criteria to participate:

1. Must be 21 years of age or older.
2. Must understand and voluntarily have signed an Informed Consent after its contents have been fully explained.
 - a. For patients highly suspected to have acute GVHD and requiring systemic therapy, informed consent should be signed prior to biopsy taken to support clinical diagnosis.
 - b. For patients at high risk for developing acute GVHD, informed consent should be signed prior to transplant.
3. For healthy volunteers only: Must have no known medical problems that would make undergoing the scan hazardous to the health of the patient or interfere with the results. In particular subjects should not have any cardiac or immunological disorders as these would likely affect the scan results. Subjects should have had a full physical exam within 6 months of the study. If healthy volunteers have not had a full medical exam within 6 months of the study, one of the nuclear medicine physicians will conduct the medical exam prior to any study procedures.
4. For patients highly suspected to have acute GVHD and requiring systemic therapy only:

Taking steroid treatment for suspected acute GVHD for 7 days or less.

5. For patients at high risk for developing acute GVHD only: Recipients of myeloablative or reduced intensity allogeneic transplants using either bone marrow or peripheral blood stem cells from HLA-matched or HLA-mismatched related or unrelated donors (protocols 9917, 9142, 9022, 9924) who have not yet been placed on any therapy for acute GVHD.

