13. Participants will undergo a safety follow-up at one time point within the time interval (day 2 – day 7) post-scan for blood sample collection for blood chemistry and hematology and also for observation for vital signs. For in-patients we will use the blood samples and vital signs

obtained as part of the standard of care by the Bone Marrow and Transplant group. Out-patients will have to return to the clinic for the safety follow up.

14. Adverse drug events will be recorded at one time point with the time interval of 2-7 days after [¹⁸F]F-AraG injection/scan in the case report form.
15. Patients in the high risk of developing GVHD arm will undergo the above protocol once more 10-17 days after the first scan.
16. A post safety follow up will be conducted for up to 6 months via chart review to assess progression or development of aGVHD.

Safety Follow-up [range: One time point within the interval (Day 2 to Day 7) post-scan

1. BP, HR, Temperature, Blood Oxygen %, and Respiratory Rate will be recorded.
2. Blood will be collected for CBC, and Metabolite Analysis.
3. Adverse events will be collected at one time point within the time interval (day 2 – day 7) post scan.

Healthy subjects and out-patients will need to come in to the clinic for the safety follow up. For in-patients (GVHD group)-we will obtain the blood samples and vital signs obtained as part of the standard of care by the Bone Marrow and Transplant group.

Subjects with suspected acute GVHD OR at high-risk of aGVHD will be followed for 6 months post their last scan to evaluate disease (progression/development) by chart-review.

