5.2 Criteria for Removal from Study

Withdrawal of Participants

The Protocol Director may withdraw participants from the study for one or more of the following reasons: failure to follow the instructions of the Protocol Director and/or the study staff; failure to provide informed consent; determination that continuing the participation could be harmful to the subject; the study is cancelled or other administrative reasons.

Discontinuation: Patients can discontinue in case of unacceptable adverse events or patient decision to withdraw from study.

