Table 6-3: Study Calendar for Patients at high risk of developing acute GHVD

a: Investigational Agent: Dose as assigned (5 mCi); route/schedule.

b: Albumin, alkaline phosphatase, total bilirubin, bicarbonate, BUN, calcium, chloride, creatinine, glucose, LDH, phosphorus, potassium, total protein, SGOT[21], SGPT[45], sodium.

c: Obtained as part of the standard of care by the Bone Marrow and Transplant group for in-patients (for in-patients)

d: Procedure may be done during screening period or on Day 1 prior to injection of study drug.

CONFIDENTIAL

- e: On Day 1: Scan 1: head to toe PET/CT scan 60 minutes post injection); OPTIONAL head to toe PET/CT scan 30-minutes post-injection;
On Day 11-18: Scan 2: head to toe PET/CT scan 60 minutes post injection); OPTIONAL head to toe PET/CT scan 30-minutes post-injection
- f: Chart review for up to 6 months post scan to monitor disease progression
- g: Collected at one time point within the time interval (day 2 – day 7) post-scan #1 and at one time point within the time interval (day 2 – day 7) post-scan #2

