- The amount of radiation dose the GVHD group will receive from one [¹⁸F]F-AraG PET/CT session is 5.7-6.3 mSv (2.7mSv from 163MBq for females and 3.3 mSv from 211MBq of [¹⁸F]F-AraG for males plus a further 3mSv from the whole body CT scans for attenuation correction. If a patient is able to withstand longer times in the scanner they will undergo a further PET acquisition at 30 minutes for which 1 more CT scans will be performed usually before the PET acquisition (and an additional 3mSv dose will be received).

This amount of radiation involves minimal risk and is necessary to obtain the research information desired. Procedures will be in place for verification of correct radiopharmaceutical dose and route of administration (i.e., each dose will be double checked for dosimetry and quality by a researcher and technologist).

Risks associated with aGVHD

Patients highly suspected to have aGVHD or who are at high risk of developing aGVHD may experience side effects from underlying disease while participating in this study. Acute GVHD is characterized by a wide spectrum of host tissue injuries in the gastrointestinal (GI) tract, liver, skin, and lungs; causing a wide range of symptoms [3, 5]. In this setting, a very large number of

Grade 1 and 2 adverse events (AEs) are expected to occur, regardless of whether or not a patient is participating in a research study. Expected AEs include a number of specific AEs that are associated with acute GVHD.

The Protocol Director (PD) or designee will assess each AE to determine whether it is unexpected according to the Informed Consent, Protocol Document, or Investigator's Brochure, and related to the investigation. Unless specifically determined otherwise by the investigator, the following events are considered expected in the early post-transplant setting.

- Alopecia
- Anemia
- Anorexia
- Bleeding, including requiring transfusions
- Cardiac arrhythmias
- Central venous catheter infections
- Constipation
- Diarrhea
- Edema
- Fatigue
- Febrile episodes
- Gastritis
- Graft failure
- Graft versus host disease
- Hematuria
- Hypertension
- Hypotension
- Hypoxia
- Incontinence
- Infections, including sepsis
- Insomnia
- Laboratory abnormalities
- Mental status changes and mood alterations
- Mucositis
- Nausea
- Neutropenia
- Pain
- Pleural effusion
- Pneumonitis
- Rash
- Seizures
- Sinusoidal obstructive syndrome
- Tachycardia
- Thrombocytopenia
- Thrombotic microangiopathy
- Tremor
- Vomiting

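### The high-risk arm's prediction model does not separate aGVHD already present at scan 2, its logistic fit may have no finite solution in 12-13 patients, and the month-24 primary completion contradicts the accrual and follow-up plan

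*Combined protocol and SAP*

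**What the plan says.** Section 10.5.2 gives the high-risk group (Arm 2) two analyses: a rank correlation between the SUVs (standardised uptake values) of the two scans, and logistic regression for "prediction of disease status at end of follow-up (aGVHD or no aGVHD) from SUV values of the first and second scans". It does not say whether the two SUVs enter one model or two, and it names no alternative to an ordinary fit.

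Scan 1 is on day 4 ± 2 after transplant (section 2.6). For scan 2, section 2.6 says "Additionally these patients will be scanned again between day 14-21 post transplant", section 5.1 says "Patients in the high risk of developing GVHD arm will undergo the above protocol once more 10-17 days after the first scan", and a footnote to Table 6-3 says "On Day 11-18: Scan 2: head to toe PET/CT scan 60 minutes post injection".

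On the outcome, section 2.6 says "Follow up on these patients will note those that go on to develop aGVHD". Section 9.1.1 says monitoring for aGVHD comes after the second scan and makes development of aGVHD the outcome variable. Section 7.2 records the date of onset and the grade.

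On disease status before scan 2, section 3.1 admits patients "who have not yet been placed on any therapy for acute GVHD", which is an enrolment criterion, with consent before transplant. Section 5.2 opens its list with "The Protocol Director may withdraw participants from the study for one or more of the following reasons"; onset of aGVHD is not on that list. Section 7.1 says "the following events are considered expected in the early post-transplant setting", and its list includes graft versus host disease.

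Section 3.5.1 sets primary completion at month 24 and section 3.6 sets study completion at month 36. Section 10.8 expects accrual over 24-36 months, and section 9.1.2 follows aGVHD subjects for 6 months after the final scan.

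**The concern.** Section 1.1 calls predictive power the ultimate goal, and this model is the only planned analysis of it. A patient whose aGVHD starts between transplant and scan 2 stays in the study, is scanned while ill, and ends follow-up classed as aGVHD. Nothing keeps that patient out of the model. If the tracer shows existing disease, the scan 2 coefficient then reflects detection but is reported as prediction.

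The fit itself is also at risk. If the SUVs divide cases from non-cases perfectly (separation), or if all patients have the same outcome, maximum likelihood gives no finite odds ratio. Separation becomes more likely the better the tracer works, and section 10.7 expects a high level of agreement between uptake and disease. No fallback is written.

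The completion dates are a separate matter: a data cut at month 24 would come before the stated follow-up is complete.

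**Working it through.** **1. Exposure to earlier onset.** Contamination of scan 2 can come from any onset between transplant and scan 2, that is, up to day 14-21 under section 2.6. The documents give neither the distribution of onset times nor the SUV rise in established disease, so the bias cannot be sized. Only its direction can be shown. Assume the tracer has no predictive value (AUC, the area under the ROC curve, is 0.50), that uptake is 2 SD higher only in patients already ill at scan 2, and that these are a share q of all cases. The apparent scan 2 AUC is then q × Φ(2/√2) + (1 − q) × 0.5, with Φ(1.414) = 0.921:
- q = 10%: 0.092 + 0.450 = 0.54
- q = 25%: 0.230 + 0.375 = 0.61
- q = 50%: 0.461 + 0.250 = 0.71

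These are illustrations, not estimates for this trial.

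**2. Chance of no finite fit.** Inputs from the documents: up to 25 patients, roughly half per group (section 10.7), so 12-13 in Arm 2; aGVHD incidence 20-50% with related donors and upwards of 70% with matched unrelated donors (section 2.1). Assumptions: one SUV summary per patient per scan (section 10.5.2 names the median or maximum across regions only for the other group); normal SUVs; a shift in cases of √2 × z(AUC) SD, for example 1.414 × 0.842 = 1.19 at AUC 0.8; correlation 0.5 between scans. Incidences of 20, 35, 50 and 70% were simulated, with 10,000 trials per cell. Failure means complete separation or a single outcome class. Ranges are over incidence, n = 12:

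| Assumed per-scan AUC | Both SUVs in one model | One SUV per model |
|---|---|---|
| 0.5 | 3-22% | 1-11% |
| 0.7 | 11-32% | 3-16% |
| 0.8 | 24-46% | 8-25% |
| 0.9 | 54-68% | 24-41% |

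At n = 13 the two-SUV column is 2-19%, 8-27%, 19-41% and 49-65%. With correlation anywhere from 0 to 0.8, the two-SUV range at AUC 0.8 (n = 12) is 21-56%.

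One-class samples are included, with probability p^n + (1 − p)^n. At n = 12 this is 0.8^12 = 6.9% at 20% incidence, 2 × 0.5^12 = 0.05% at 50%, and 0.7^12 = 1.4% at 70% (the other term is negligible at 20% and 70%). Separation alone at AUC 0.8 is 24-39% (both SUVs) or 8-18% (one SUV).

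Two checks. With no association and 50% incidence, Cover's formula for two predictors gives 2 × (1 + 11 + 55)/2^12 = 134/4096 = 3.3% at n = 12, against 3.1% in a separate simulation with a linear-programming test. That second simulation gave 19-40% at a joint AUC of 0.79 and 31-50% at 0.86 (n = 12). A per-scan AUC of 0.8 with correlation 0.5 is a joint AUC of about 0.83, and 24-46% lies between them.

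**3. Dates.** Stated primary completion: month 24. From the plan's own inputs: 24 + 6 = 30 months at the shortest planned accrual and 36 + 6 = 42 at the longest. These are slightly low, because scan 2 follows entry by some weeks. Completion at month 24 would need the last scan by 24 − 6 = month 18, before the earliest planned end of accrual. Month 42 also passes the month-36 study completion.

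**The case against.** The best counter-argument is section 9.1.1, which places monitoring after the second scan; section 2.6 points the same way by speaking of patients who later develop aGVHD. A landmark may well have been intended. That stands as evidence of intent, but neither section says whether a patient with earlier onset is dropped, counted as a case, or counted otherwise, and section 10.5.2 has no restriction.

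Second, this is a pilot that admits low power in sections 10.5.2 and 10.7, plans descriptive statistics, and sets no decision threshold on this model. A failed fit would be visible to the analyst. This limits the severity. It does not remove the point: low power means a wide interval, whereas separation means no finite estimate.

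Third, the failure rates rest on an assumed AUC and on the number of SUVs per model, and the plan fixes neither. That stands. A reader might infer that the model will usually fail; the documents do not support that. The rate is lower for a weaker tracer or one SUV per model, and one-class samples cannot be rescued by any regression.

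Fourth, 25 is a maximum, and section 5.1 says chart review lasts up to 6 months, so a smaller or faster study could finish earlier. That is not the accrual and follow-up that sections 10.8 and 9.1.2 state.

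Three further readings are tempting but unsupported:
- That early onsets go unrecorded: section 7.2 collects the onset date, and section 9.1.1 grades disease at imaging.
- That the end-of-follow-up wording reclassifies resolved cases as disease-free: sections 2.6, 7.2, 9.1 and 9.1.1 all refer to development of aGVHD.
- That the scan 2 windows are incompatible: combining 10-17 days after scan 1 with day 14-21 leaves days 14-19 if scan 1 is on day 2, 14-21 if on day 4, and 16-21 if on day 6. Table 6-3 restates the interval with scan 1 as day 1 (1 + 10 = 11, 1 + 17 = 18). Consistent wording is all that is needed.

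**Conclusion.** The point holds as a pre-specification gap that should be fixed. As written, the plan allows detection of existing aGVHD at scan 2 to be reported as prediction. The direction is clear if uptake rises with established disease; the size cannot be derived from the documents.

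The named method also carries a material risk of giving no finite estimate: about 24-46% with both SUVs or 8-25% with one SUV, at n = 12, incidence 20-70%, assumed AUC 0.8 and (for two SUVs) assumed correlation 0.5, one-class samples included.

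The month-24 primary completion contradicts the stated accrual and follow-up, which give about 30-42 months. This part needs no assumption beyond the plan's own figures.

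A reader might infer that the study is invalid or its sample size wrong. Neither follows: it is an exploratory pilot, no sample size is derived, and descriptive results remain available.

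**What to change.** In section 10.5.2:
1. Count as events only aGVHD onsets after the scan used as predictor. Restrict the scan 2 prediction analysis to patients free of aGVHD at scan 2 by recorded onset date. Report earlier onsets descriptively, as detection.
2. Fit each scan in its own model by Firth logistic regression with profile-likelihood 95% intervals. If all patients in an analysis share one outcome, report descriptively only. Label these analyses exploratory.

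In sections 3.5.1 and 3.6, restate primary and study completion so that they follow from accrual plus 6 months of follow-up, and align them with sections 9.1.2 and 10.8. Word the scan 2 timing consistently in sections 2.6 and 5.1 and Table 6-3.

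The cost is wording and dates; the onset date is already collected. There are statistical downsides:
- **Fewer events in the scan 2 analysis.** If 10, 25 or 50% of onsets (assumed) precede scan 2, 12 patients at 50% incidence give 6 × 0.90 = 5.4, 6 × 0.75 = 4.5 or 6 × 0.50 = 3 events. At 20% incidence, 2.4 becomes 2.2, 1.8 or 1.2, and the chance of no later event is 0.82^12 = 9%, 0.85^12 = 14% or 0.90^12 = 28%.
- **Shrinkage.** With one SUV and n = 12, the simulated median Firth log odds ratio per SD is 0.98-1.04 against a true 1.19 at AUC 0.8, and 1.34-1.44 against 1.81 at AUC 0.9. Interval coverage was 95-97%.
- **Wide intervals.** At AUC 0.8 and 50% incidence, the median interval runs from about 0 to 3 in all 12 patients, and from about −0.4 to 3.5 in the scan 2 set if half of onsets come first.
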